9.4. Data sources

This study will be implemented using health care data source partners in VAC4EU from countries where the Pfizer-BioNTech COVID-19 bivalent vaccine will be available. A preliminary list of these partners, to be confirmed, based on availability, is as follows:

- **Italy:** PEDIANET
 - Pedianet is a paediatric general practice research data source containing health care data for children seen by approximately 140 paediatricians distributed throughout Italy. Pedianet can link to other data sources, including those containing information on routine childhood vaccination and hospitalisation. The family paediatrician's participation in the database is voluntary, and individuals and their parents provide consent for use of their data for research purposes. This database will be the only one not contributing data for the assessment of pregnancy outcomes.
- **The Netherlands:** PHARMO Database Network
 - The PHARMO Database Network, which is maintained by the PHARMO Institute for Drug Outcomes Research, is a population-based network of EHR data sources that combines anonymous data from different primary and secondary health care settings in the Netherlands. Currently, the PHARMO Database Network covers over 7 million active individuals out of a total of 17 million inhabitants in the Netherlands.³² The General Practitioner Database contains data from 2.0 million active individuals. The records include information on diagnoses and symptoms, laboratory test results, referrals to specialists and health care product/drug prescriptions. In the PHARMO Network data on vaccinations administered by general practitioners and by the public health service are available. PHARMO general practitioner data are representative of the Dutch population in terms of demographic characteristics and diagnoses in primary care.³³
- **Norway:** Norwegian Health Registries (NHR)
 - The Norwegian Health Registries (NHR), accessed through a partnership with the University of Oslo, cover several national health registers, ie, the Medical Birth Registry of Norway (MBRN), the National Patient Register (NPR), Norway Control and Payment of Health Reimbursement (KUHR), the Norwegian Immunisation Registry (SYSVAK), the Norwegian Prescription Database (NorPD), and Statistics Norway (SSB). These data sources cover virtually the entire population of Norway, with 5.3 million active individuals.
- **Spain:** EpiChron and SIDIAP
 - **EpiChron:** The EpiChron Cohort Study links socio-demographic and clinical anonymised information for all the inhabitants of Aragon region, built from the BIGAN platform. The Aragon BIGAN platform integrates a technical infrastructure and a data lake

gathering individual data from the regional health service information systems, including primary care, specialised care, hospitalisations, ER episodes, drug prescriptions, image diagnosis, laboratory tests, diagnostics, vaccination, medical history and demographics from the users of the public health system of Aragon, about 2 million individuals with historic data, and an active population of 1.3 million individuals.

- SIDIAP:** The Information System for the Improvement of Research in Primary Care (Sistema d’Informació per al Desenvolupament de la Investigació en Atenció Primària’ [SIDIAP]) SIDIAP includes data from 328 primary care centres managed by the Catalan Health Institute in Catalonia, Spain. The database contains pseudo-anonymised records for >8 million people since 2006, with 5.8 million people active in June 2021 (75% of the Catalan population). SIDIAP is representative of the general population living in Catalonia in terms of age, sex and geographic distribution ³⁴. SIDIAP includes data on the clinical and referral events registered by primary health care professionals and administrative staff in EHRs, demographic information, community pharmacy invoicing data, specialist referrals, and primary care laboratory test results. SIDIAP data can be linked to other data sources and registers at the local and national level.
- UK: Clinical Practice Research Datalink (CPRD)**

 - CPRD includes data from EHRs of general practitioners in the UK who act as gatekeepers for health care and maintains individuals’ life-long EHRs. Secondary care teams also provide information to general practitioners about their patients, including key diagnoses and procedures. The data recorded in the CPRD include demographic information, prescription details, clinical events, preventive care, specialist referrals, hospital admissions, and major outcomes, including death. Currently, CPRD Aurum contains data for approximately 13.3 million individuals [Current acceptable individuals (ie, registered at practices currently contributing data, excluding transferred out and deceased individuals)].

9.5. Study size

The study size will be determined by the uptake of the bivalent BA.1 and bivalent BA.4-5 vaccines in the contributing data sources during the study period. The 95% confidence intervals ³⁵ for different potential values of the true risk ratios of the AESIs are shown in Table 3, under different scenarios of risks in the unvaccinated population and of sample sizes, assuming complete follow-up.

Table 3. Confidence interval limits for AESI risk ratios for different scenarios of true risks in the unvaccinated group and various sample sizes

Number of individuals per group (sample size)	AESI risk in unvaccinated group	Risk ratio	Lower bound of 95% CI	Upper bound of 95% CI
10,000	1 per 100,000	2	<0.01	3960.57
		5	0.01	4442.71

PFIZER CONFIDENTIAL

Table 3. Confidence interval limits for AESI risk ratios for different scenarios of true risks in the unvaccinated group and various sample sizes

Number of individuals per group (sample size)	AESI risk in unvaccinated group	Risk ratio	Lower bound of 95% CI	Upper bound of 95% CI	
	1 per 50,000	10	0.02	6654.91	
		2	0.01	428.70	
		5	0.04	608.11	
	1 per 5000	10	0.10	991.39	
		2	0.37	10.92	
		5	1.10	22.81	
	100,000	1 per 100,000	10	2.34	42.77
			2	0.18	22.06
			5	0.58	42.80
1 per 50,000		10	1.28	78.12	
		2	0.37	10.92	
		5	1.10	22.82	
1 per 5000		10	2.34	42.78	
		2	1.17	3.42	
		5	3.09	8.08	
1,000,000	1 per 100,000	10	6.32	15.83	
		2	0.94	4.27	
		5	2.54	9.86	
	1 per 50,000	10	5.22	19.16	
		2	1.17	3.42	
		5	3.09	8.08	
	1 per 5000	10	6.32	15.84	
		2	1.69	2.37	
		5	4.30	5.82	
		10	8.65	11.56	

AESI: adverse event of special interest. CI: confidence interval.

9.6. Data management

This study will be conducted in a distributed manner using a common protocol, common data model (CDM), and common analytics programs using existing health care data. The following steps will be implemented:

Step 1: Extraction, transformation, and loading (ETL) of data to the CDM. A shared syntactic foundation will be used to harmonise the structure of the data sets stored and maintained by each data access provider (DAP). The CDM developed during the IMI-ConcePTION project will be used.³⁶ In this CDM, data are represented in a common structure, but the content of the data remain in their original format. The ETL design for each study will be shared in a searchable findable, accessible, interoperable, and re-usable (FAIR) catalogue. FAIR is defined as findable, accessible, interoperable, and re-usable. The VAC4EU FAIR data catalogue is a meta-data management tool designed to contain searchable meta-data describing organisations that can provide access to specific data sources. Data quality checks

[figure not shown]
PFIZER CONFIDENTIAL

will be conducted to measure the integrity of the ETL as well as the internal consistency within the context of the CDM (see [Section 9.8](#)).

Step 2: Reconcile differences between terminologies. A shared semantic foundation will be built for the definition of the events to be analysed by collecting relevant concepts in a structured fashion using a standardised event definition template to reconcile differences between terminologies. The CodeMapper tool was used to create diagnosis code lists based on completed event definition templates for each AESI and comorbid risk condition in the ACCESS project.⁶ Based on the relevant diagnostic medical codes and keywords, as well as other relevant concepts (eg, medications), one or more algorithms will be constructed (typically one sensitive, or broad, algorithm and one specific, or narrow, algorithm) to operationalise the identification and measurement of each event. These algorithms may differ between data sources, as the components involved in the study variables may differ. Manual review of electronic records will be conducted for a sample of the events. Specifications for both ETL and semantic harmonisation will be shared in the catalogue.

Step 3: Conversion to harmonised study variable sets. R and SAS programs for the calculation of incidence and prevalence rates will be distributed to DAPs for local deployment after conversion to harmonised study variable sets. The aggregated results produced by these scripts will then be uploaded to the Digital Research Environment (DRE) for pooled analysis and visualisation (Figure 3) The DRE will be made available through UMCU (University Medical Center Utrecht)/VAC4EU (<https://www.andrea-cloud.eu/>). The DRE is a cloud-based, globally available research environment where data are stored and organised securely and where researchers can collaborate (<https://www.andrea-cloud.eu/azure-dre/>).

Figure 3. Data management plan

CDM = common data model.

090177e19fa902a7Approved\Approved On: 12-Jan-2024 21:20 (GMT)

9.6.1. Case report forms (CRFs)/Data collection tools (DCTs)/Electronic data record

This study will use secondary data collected from EHR databases. Specific forms will be developed for the validation of selected study endpoints and securely saved in environments assuring data protection and participant confidentiality according to the requirements of each country and DAP.

As used in this protocol, the term CRF should be understood to refer to either a paper form or an electronic data record or both, depending on the data collection method used in this study.

A CRF is required and should be completed for each included participant. The completed original CRFs are the sole property of the DAPs and should not be made available in any form to third parties, except for authorised representatives of Pfizer or appropriate regulatory authorities. The DAPs shall ensure that the CRFs are securely stored at the study site in encrypted electronic form and will be password protected to prevent access by unauthorised third parties.

The DAPs have ultimate responsibility for the collection and reporting of all clinical, safety and laboratory data entered on the CRFs for the procedure of event/case verification/validation and ensuring that they are accurate, authentic/original, attributable, complete, consistent, legible, timely (contemporaneous), enduring, and available when required. The CRFs must be signed by an authorised staff member at the DAP to attest that the data contained on the CRFs are true. Any corrections to entries made in the CRFs or source documents must be dated, initialed, and explained (if necessary) and should not obscure the original entry.

The source documents are the hospital or physician's charts. In these cases, data collected on the CRFs must match those charts. Each DAP will follow its own specific validation procedures, aligned to the general VAC4EU validation plan.

9.6.2. Record retention

The final study aggregated results sets and statistical programs will be archived and stored on the DRE and the VAC4EU SharePoint site. Validation of the quality control (QC) of the statistical analyses will be documented. The final study protocol and any amendments, the final statistical analysis plan, statistical programs, and output files will be archived on a specific and secured central drive. Study records or documents may also include the analyses files, syntaxes (usually stored at the data source site), ETL specifications, and output from data quality checks.

To enable evaluations and/or inspections/audits from regulatory authorities or Pfizer, DAPs agree to keep all study-related records, including the identity of all participating individuals (sufficient information to link records, eg, CRFs and hospital records), copies of all CRFs, safety reporting forms, source documents, detailed records of treatment disposition, and adequate documentation of relevant correspondence (eg, letters, meeting minutes, and telephone call reports). The records should be retained by DAPs according to local

regulations or as specified in the vendor contract, whichever is longer. DAPs must ensure that the records continue to be stored securely for so long as they are retained.

If UMCU, for any reason becomes unable for any reason to continue to retain study records for the required period, Pfizer should be prospectively notified. The study records must be transferred to a designee acceptable to Pfizer, such as another DAP, another institution, or to an independent third party arranged by Pfizer.

Study records must be kept for a minimum of 15 years after completion or discontinuation of the study, unless UMCU and Penta and Pfizer have expressly agreed to a different period of retention via a separate written agreement. Records must be retained for longer than 15 years or as required by applicable local regulations.

UMCU must obtain Pfizer's written permission before disposing of any records, even if retention requirements have been met.

9.6.3. Data processing and transformation

The R and SAS scripts will first transform the data in the syntactically harmonised CDM to semantically harmonised study variables (Figure 2). Following creation of study variables, the data will be characterised. This characterisation will include calculation of code counts and incidence rates, as well as benchmarking within the data source (over time), between data sources and externally (against published estimates). Subsequently, R and SAS scripts to conduct analysis against semantically harmonised study variables will be distributed and run locally to produce aggregated results. The R and SAS scripts for these processing and analysis steps will be developed and tested centrally at UMCU and sent to the DAPs.

The R and SAS scripts will be structured in a modular format to ensure transparency. Functions to be used in the modules will be either standard R and SAS packages or packages specifically designed, developed, and tested for multi-database studies. Scripts will be double coded in SAS and R and quality checks will be thoroughly documented.

The DAPs will run the R and SAS scripts locally and send aggregated analysis results to the DRE using a secure file transfer protocol. In the DRE, results will be further plotted, inspected (for quality assessment), and pooled (if needed) for final reporting.

All final statistical computations will be performed on the DRE using R or SAS. DAPs will have access to the workspace for script verification.

Aggregated results, ETL specifications, and a repository of study scripts will be stored in the DRE.

9.6.4. Data access

Within the DRE, each project-specific area will consist of a separate secure folder called a workspace. Each workspace will be completely secure, and researchers will be in full control

of their data. Each workspace will have their own list of users, which will be managed by its administrators.

The DRE architecture will allow researchers to use a solution within the boundaries of data management rules and regulations. Although General Data Protection Regulation and Good (Clinical) Research Practice still apply to researchers, the DRE offers tools to more easily control and monitor which activities take place within projects.

All researchers who need access to the DRE will be granted access to study-specific secure workspaces. Access to these workspaces will only be possible via a double authentication process, using an identification code and password together with the user's mobile phone for authentication.

All researchers with access to the workspace within the DRE will be able to upload files. Downloading of files will only be possible after requesting and receiving permission from a workspace member with an 'owner' role.

9.7. Data analysis

Detailed methodology for summary and statistical analyses of data collected in this study will be documented in a statistical analysis plan (SAP), which will be dated, filed, and maintained by the sponsor. The SAP may modify the plans outlined in the protocol; any major modifications of primary endpoint definitions or their analyses will be detailed in a protocol amendment.

Data will be extracted and descriptive and comparative analyses (when informative) for all AESIs, except major congenital anomalies, from study start (ie, September 2022, at the earliest) up to the latest data available in each data source will be reported in the interim report (14 May 2025). For the final report (30 April 2026), additional data extraction and analyses of all outcomes, including major congenital anomalies, will be done up to 30 September 2025 or the latest data available in each data source.

9.7.1. Cohort design

9.7.1.1. Exposure assignment and follow-up

The main exposure of interest is in the receipt of at least one dose of the bivalent BA.1 or bivalent BA.4-5 vaccine. Individuals will be assigned to each vaccination category according to their data at time zero, as outlined below:

- **Exposed cohort:** Individuals will be assigned to this cohort when they receive a first dose of the bivalent BA.1 or bivalent BA.4-5 vaccine. Individuals will be censored if they receive a non-Pfizer COVID-19 vaccine during follow-up. For the matched comparative analyses individuals will be censored when their matched pair is censored.
- **Unexposed cohort:** Individuals will be assigned to this cohort if they have not received a COVID-19 vaccine at time zero. Individuals will be censored if and when

PFIZER CONFIDENTIAL

they receive a dose of any COVID-19 vaccine during follow-up. Time zero in the unexposed cohort will be the same day when they did not receive a Pfizer-BioNTech COVID-19 vaccine dose. This day will be chosen by calendar matching to the time zero of the corresponding exposed group.

Individuals will be followed from time zero (see [Section 9.1.1.4](#)) until the censoring described above, death, administrative end of follow-up, or end of study period 31 August 2024, whichever occurs first, with pregnancies followed until 30 June 2025 (see [Section 9.7.1.7](#)). For analyses of AESIs with known risk intervals, follow-up will be truncated at the end of the risk interval.

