9.1.1.4. Follow-up

Individuals will be followed from time zero until the end of the study period (31 August 2024, or 30 June 2025 for pregnancy outcomes), the occurrence of the AESI being analysed, death, or disenrollment from the data source, whichever occurs first. Additionally, the

PFIZER CONFIDENTIAL

CT24-WI-GL02-RF02 4.0 Non-Interventional Study Protocol Template For Secondary Data Collection Study

01-Jun-2022

Page 18 of 64

matched pair will be censored when the unexposed individual of the pair receives any COVID-19 vaccine or when the exposed individual in the pair receives a non-Pfizer vaccine.

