9.3.2. Outcomes

The list of AESIs to be analysed as outcomes and the preferred study design are based on those proposed by the EMA -sponsored ACCESS project (vACCine COVID-19 monitoring readinESS) and also, for consistency, those included in the ongoing PASS of the Pfizer BioNTech COVID-19 monovalent vaccine (EUPAS41623). The AESIs are listed in Table 1 by body system, with the corresponding risk interval and preferred study design (Section 9.1). Clinical validation will be considered for specific AESIs.

Table 1. Safety outcomes: adverse events of special interest (AESIs) with estimated risk intervals and preferred study design

Body system / classification	Adverse event of special interest	Estimated risk interval (days)*	Preferred study design*
Autoimmune diseases	Guillain-Barré syndrome ^a	42	Cohort/SCRI
	Acute disseminated encephalomyelitis	42	Cohort/SCRI
	Narcolepsy ^a	42	Cohort/SCRI
	Acute aseptic arthritis	42	Cohort/SCRI
	Diabetes mellitus type 1	365	Cohort
	(Idiopathic) thrombocytopenia ^a	42 ^a	Cohort/SCRI
	Thrombosis thrombocytopenia syndrome (TTS) ^a	15 ^a	Cohort/SCRI
	Myositis	365	Cohort
Cardiovascular system	Acute cardiovascular injury including microangiopathy	365	Cohort
	Arrhythmia	365	Cohort
	Heart failure	365	Cohort
	Stress cardiomyopathy	365	Cohort
	Coronary artery disease	365	Cohort
	Myocarditis or pericarditis ^a	7; 14; 21	Cohort/SCRI
	Myocarditis ^a	7; 14; 21	Cohort/SCRI
	Pericarditis ^a	7; 14; 21	Cohort/SCRI
Circulatory system	Coagulation disorders: thromboembolism, haemorrhage	28	Cohort/SCRI

PFIZER CONFIDENTIAL

CT24-WI-GL02-RF02 4.0 Non-Interventional Study Protocol Template For Secondary Data Collection Study

01-Jun-2022

Page 23 of 64

090177e19fa902a7Approved\Approved On: 12-Jan-2024 21:20 (GMT)

Table 1. Safety outcomes: adverse events of special interest (AESIs) with estimated risk intervals and preferred study design

Body system / classification	Adverse event of special interest	Estimated risk interval (days)*	Preferred study design*
	Single organ cutaneous vasculitis	28	Cohort/SCRI
	Cerebral venous sinus thrombosis	28 ²⁸	Cohort/SCRI
Hepato-gastrointestinal and renal system	Acute liver injury	365	Cohort
	Acute kidney injury	365	Cohort
	Acute pancreatitis	365	Cohort
	Rhabdomyolysis	365	Cohort
	Glomerulonephritis	365	Cohort
Nerves and central nervous system	Generalised convulsion	42	Cohort/SCRI
	Meningoencephalitis	42	Cohort/SCRI
	Transverse myelitis ^a	42	Cohort/SCRI
	Bell's palsy	42	Cohort/SCRI

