9.7.1.4. Crude outcome measures

For safety outcomes with a known short risk interval ([Table 1](#)) (e.g., anaphylaxis), the risk (number of events/number of individuals in a cohort) and the corresponding 95% CIs will be computed. Effect estimates will be calculated both as risk differences and as risk ratios, with their corresponding 95% CIs, for those exposed to a Pfizer-BioNTech COVID-19 bivalent vaccine compared with the unexposed group that did not receive any COVID-19 vaccine during follow-up.

For safety outcomes with unknown risk intervals or those that require long follow-up (eg, death), the cumulative incidence will be computed, which will be estimated using the 1 – Kaplan-Meier estimator. Time to outcome will be defined as the time from the baseline date (time zero) until the occurrence of the outcome or censoring (Section 9.1.1.4 and Section 9.7.1.7). The variance will be computed using approaches that account for autocorrelation (eg, the robust estimator or via bootstrapping).^{39,40} Risk differences and risk ratios (and their corresponding 95% CIs) will be estimated at different time intervals, which will be adapted to the specific nature of each outcome.

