9.9. Limitations of the research methods

This study is subject to limitations related to both the study design and to the use of secondary health care data.

A data-related limitation of this study is the reliance on the accuracy of codes and algorithms to identify outcomes. Some outcomes and their dates of occurrence will be validated, but the extent of validation may be limited because of only partial access to medical records. It is

possible that some AESIs may be due to immunisation errors occurring during the administration of the bivalent BA.1 or bivalent BA.4-5 vaccines. This information is not regularly collected and it will not be possible to take these events into account with the current protocol. Exposure identification may be based on pharmacy dispensing records, general practice records, immunisation registers, medical records, or other secondary data sources. How specific COVID-19 vaccine products and dates of vaccination in these data sources will be identified is described in [Section 9.3.1](#). It is possible that vaccination of individuals outside the health care system will not be recorded in secondary EHR databases, thereby leading to potential bias because of exposure misclassification. Additionally, while every effort will be made to capture data on all variables, some data may not be identified or recorded in the data sources.

A study design-related limitation of both the cohort and SCRI designs is that any uncertainty regarding risk periods will lead to misclassification and underestimation of the risk. The estimation of cumulative incidence curves with a time zero starting on the date of the exposure assignment and eligibility assessment will minimise the impact of unknown risk periods, because there is an unvaccinated comparator and evaluation is done over the whole available follow-up.

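### The whole-follow-up safeguard in Section 9.9 does not cover AESIs analysed only within an estimated short risk window, and Table 1 does not say which those are

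*Protocol*

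**What the plan says.** Four parts of the protocol bear on how long the cohort is observed for each AESI.

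- **Section 9.1.1.4** gives the general rule: follow-up from time zero to the end of the study period, the AESI, death or disenrolment, with pair censoring for certain vaccinations. It does not mention truncation.
- **Section 9.7.1.1** refers to 9.1.1.4, restates follow-up to study end, and then adds an exception: "For analyses of AESIs with known risk intervals, follow-up will be truncated at the end of the risk interval".
- **Section 9.7.1.4** splits the measures the same way. "For safety outcomes with a known short risk interval", the measure is events divided by individuals. By contrast, "For safety outcomes with unknown risk intervals or those that require long follow-up (eg, death), the cumulative incidence will be computed", using one minus Kaplan-Meier.
- **Section 9.9** says of both designs that "any uncertainty regarding risk periods will lead to misclassification and underestimation of the risk". The next sentence offers the remedy: cumulative incidence curves "will minimise the impact of unknown risk periods, because there is an unvaccinated comparator and evaluation is done over the whole available follow-up".

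Table 1 (Section 9.3.2) supplies the intervals. Its column heading calls them estimated, and no row is labelled known or unknown. Its footnote says that a 42-day interval means follow-up from the day of vaccination to day 41. Section 9.7.2.2 sets the SCRI control period to the same length as the risk interval and places it after that interval.

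**The concern.** A misjudged window does harm where a window is imposed. Those are the AESIs for which the cohort stops counting at the end of the window and the SCRI compares the window with the period after it. Section 9.9 states the limitation without restriction, yet the remedy it gives works only where follow-up is not cut. If the short intervals in Table 1 count as known, they bear the limitation and do not get the remedy.

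The AESIs concerned include Guillain-Barré syndrome, TTS, myocarditis, cerebral venous sinus thrombosis and Bell's palsy. For these, an excess arising or recorded after the window would be missing from the cohort estimate and could pull the SCRI estimate down. A null result could then be defended by citing a protection that the analysis of that AESI did not contain.

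**Working it through.** **1. Which AESIs are concerned.** Counting the non-pregnancy rows of Table 1 that have a numeric interval:

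| Longest listed interval | AESIs |
|---|---|
| 42 days | 13 |
| 28 days | 3 |
| 21 days (listed as 7; 14; 21) | 3 |
| 15 days | 1 |
| 1 day | 1 |
| **42 days or less** | **21** |
| 183 days | 2 |
| 365 days | 16 |
| **Total** | **39** |

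Severe COVID-19 has the entry Any. Of the 21, 17 also have the SCRI. Four are cohort only: erythema multiforme, chilblain-like lesions, anosmia/ageusia and multisystem inflammatory syndrome.

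**2. What each reading of known does.**

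- If every numeric interval is known, all 39 are truncated, including those at 183 and 365 days (the longest possible follow-up, 1 September 2022 to 31 August 2024, is 730 days). Among the non-pregnancy AESIs, only severe COVID-19 keeps its whole follow-up.
- If only the short intervals are known, the 21 are truncated and the 9.9 sentence applies to the rest.
- If estimated means not known, 9.7.1.4 would send the 21 to cumulative incidence, and the simple-risk rule would have few or no outcomes to apply to, although that section names anaphylaxis as its example.

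The protocol does not choose among these.

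**3. Share of a vaccine-related excess that falls inside the window.** The protocol gives no onset distribution. As an assumption, take exponential onset or recording with mean m of 28 or 42 days. Then share captured = 1 − exp(−w/m), where w is the longest listed window:

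| w (days) | m = 28 | m = 42 |
|---|---|---|
| 42 | 1 − exp(−1.50) = 78% | 1 − exp(−1.00) = 63% |
| 28 | 1 − exp(−1.00) = 63% | 1 − exp(−0.67) = 49% |
| 21 | 1 − exp(−0.75) = 53% | 1 − exp(−0.50) = 39% |
| 15 | 1 − exp(−0.54) = 41% | 1 − exp(−0.36) = 30% |

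Anaphylaxis (1 day) is left out because a delayed-onset model does not fit it.

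**4. Whether the SCRI fills the gap.** Assume a rate ratio of 5 while risk is raised, a 42-day risk interval, and a 42-day control period straight after it (9.7.2.2 mentions no gap).

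- True risk period 63 days: share of excess captured 42/63 = 67%; SCRI rate ratio 5 × 42 / (5 × 21 + 21) = 1.67.
- True risk period 84 days: share captured 42/84 = 50%; SCRI rate ratio 5 × 42 / (5 × 42) = 1.0.
- All excess in days 42 to 83: truncated cohort risk ratio 1.0; SCRI rate ratio 1/5 = 0.2; 365-day cohort risk ratio 1 + 4 × 42/365 = 1.46.

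In the last two cases the SCRI shows no effect or a reversed one. The cost of longer follow-up is the same arithmetic: a true effect of 5 confined to the first 42 days also dilutes to 1.46 at 365 days.

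No figure in Section 9.5 depends on this point.

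**The case against.** A reader might infer that 9.7.1.1 and 9.9 contradict each other, or that the safeguard does not exist. The text does not support that. Section 9.9 speaks of unknown risk periods, 9.7.1.1 of known intervals, and 9.7.1.4 uses the same split, so the three can be read together. Section 9.1.1.4 is not a rival rule either: 9.7.1.1 cites it and states truncation as an exception, and the Table 1 footnote agrees. The safeguard remains for outcomes that are not truncated.

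A reader might also put the understatement as high as 85%, by applying the 7-day window with a mean of 42 days (1 − exp(−7/42) = 15% captured). That is not fair to the plan. Only the three myocarditis/pericarditis rows list 7 days, and they also list 14 and 21, which is itself a limited check on the choice of window.

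Lastly, longer curves have real drawbacks. They dilute short-window effects, and Section 9.7.1.7 says the total effect depends heavily on pandemic activity during follow-up, so they take in more COVID-mediated events. Section 9.7 leaves detail to an SAP that is not at hand and may classify the intervals.

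What remains is that 9.9 concedes bias from any uncertainty and does not say that its remedy omits the truncated AESIs, while Table 1 gives no means of telling which those are. That is a claim made in the protocol itself, not a detail left to the SAP.

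**Conclusion.** The point holds as a gap in scope. If the 21 AESIs with windows of 42 days or less are treated as known, evaluation over the whole follow-up does not protect them against a misjudged window, and the SCRI does not make up for it. The protocol does not say whether they are so treated.

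The size cannot be fixed from the protocol. Under the assumed exponential onset with mean 28 or 42 days, the part of the excess missed at the longest listed window runs from 22% (42-day window, mean 28) to 70% (15-day window, mean 42). These figures illustrate the mechanism and do not estimate the bias for any AESI. If onset is confined to the listed windows, nothing is lost.

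**What to change.** 1. Keep the risk-interval estimate as the main cohort result.
2. In 9.7.1.1 and 9.7.1.4, add for the AESIs with intervals of 42 days or less a supplementary cumulative incidence curve, with risk differences and risk ratios, beyond the window and to day 365 where follow-up allows. Anaphylaxis may be left out.
3. Mark in Table 1 which intervals are treated as known and truncated, and cross-refer to the truncation from 9.1.1.4.
4. Limit the 9.9 sentence to analyses that are not truncated.

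Items 3 and 4 are wording only. Item 2 needs further runs of the planned cumulative-incidence analysis and no new data source, since 9.1.1.4 already provides for follow-up to study end. The price is more output that is noisier, dilutes a true short-window effect and includes more COVID-mediated events. The curves should therefore be labelled supplementary and read as a check for late excess, not as a second main result.
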